2.17.2 Laboratory and Vital Sign Parameter Analyses

Laboratory parameters (central) and vital signs will be summarized descriptively using the SS by treatment arm for each scheduled visit where the parameter is measured. Both the observed value and the change from baseline will be summarized. The summary of laboratory parameters will be provided for the Blinded Treatment Phase in the SS. The incidence of central laboratory test results in ranges of interest will be summarized by treatment group in the SS. These summaries will include but are not limited to the following:

- Serum potassium < 3.0, < 3.5, < 3.8, > 5.0, and \geq 5.5 mEq/L
- Serum magnesium < 1.4, < 1.2, and < 1.0 mg/dL

- Serum calcium > 10.2 mg/dL

Central laboratory shift tables from Baseline to End of Study in the SS will be provided for selected laboratory results.

Decline in eGFR > 50%, or end-stage renal disease (ESRD), or renal death, or need for dialysis at any time after randomization will be summarized by count (%). If the number of subjects experiencing this composite endpoint is sufficient, Kaplan-Meir curves for each treatment arm in the SS will also be provided.

Listings will include results from local and central labs, at both scheduled and unscheduled visits.

Listings will be provided for all serum chemistry parameters, hematology, urinalysis, urine ACR, NT-proBNP, and high sensitivity troponin. Listings of all blood pressure, heart rate, weight, and height data will be provided.

2.17.3 *Death*

A listing of all deaths will be provided. The listing will include date of death, primary cause of death and any associated AEs.

2.17.4 *Physical Examination*

Abnormalities found in physical examinations will be summarized in the SS by treatment group at Screening and at EoS/ET visit.

A listing for all physical examination data will be provided.

2.17.5 *12-lead Electrocardiogram (ECG)*

Number and percentage of subjects with normal/abnormal and clinically significant abnormal ECG findings at screening will be summarized in the SS.

A listing for all 12-lead ECG data will be provided.

2.17.6 *Special Situation*

A listing will be provided for all reported special situations.

2.17.7 *Pregnancy Reports*

A listing for all pregnancy tests will be provided.

A listing for all reports on exposure to medicine during pregnancy will be provided.

2.18 *Interim Analysis and Data Monitoring*

An independent Data and Safety Monitoring Board (DSMB) will meet periodically to monitor the study.

As part of these reviews, the DSMB will receive summaries of study conduct measures as well as unblinded safety data. No interim analysis for efficacy will be conducted.

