a. For BNP and NT-proBNP inclusion criteria in relation to the presence or not of hospitalization for HF within 12 months and the presence or not of atrial fibrillation when blood samples were collected see Section 5.2.

b. Hyperkalemia or normokalemia defined by 2 local serum K^+ values each obtained from a separate venipuncture, e.g., one in each arm. If 1 serum potassium value is hyperkalemic ($>5.0 \text{ mEq/L}$) and 1 value is normokalemic ($\leq 5.0 \text{ mEq/L}$), then a third peripheral venipuncture is performed within 1 day to obtain clarity whether a subject is hyperkalemic or normokalemic.

c. Start at 8.4 g/day and up-titrate as necessary up to 25.2 g/day. Hyperkalemic subjects start patiromer immediately; normokalemic subjects start at Week 1 or later. Subject must return within 1 week (3 days) after patiromer initiation or dose adjustments to assess potassium levels.

d. Initiate/optimize selected MRA; up-titrate to 50 mg/day. For subjects not on an MRA, the Investigator determines which MRA to initiate, and also determines the starting dose. For subjects who are on $<50 \text{ mg/day}$ of MRA, double their current dose up to 50 mg/day. Assess tolerance to the 50 mg target dose

e. If there are changes to ACEi, ARB, ARNi and/or MRA dose or serum potassium varies outside the intended range, unscheduled weekly or monthly visits should occur until stability returns.

f. If the Potassium Assessment Visit is at 2 weeks after the EoS Visit, then Follow-up phone call is not required.

SCHEDULE OF EVENTS

Procedures	Screening Phase	Run-in Phase (Single-Blinded)	Treatment Phase (Double-Blinded)										U Visit ⁽⁵⁾
	Screening Visits ⁽¹⁾	Run-in Visits ⁽²⁾ (Up To 12 wks)	Day 1/ Baseline	Day 3 (±1 D)	Week 1 (±3 D)	Week 2 (±3 D)	Week 6 (±14 D)	Week 18 (-30 D), First Every 3 Months Visit	Every 3 Months Visits After Week 18 Until EoS (-30 D)	EoS/ET Visit	PA Visit ⁽³⁾ (Up to 2 Wks)	Follow-up Phone Call (at Least 2 Wks After EoS) ⁽⁴⁾	
Informed consent	X												
IWRS entry	X	X	X	X	X	X	X	X	X	X	X	X	X ⁽²⁴⁾
Eligibility criteria	X	X ⁽⁶⁾	X ⁽⁶⁾										
Demographics	X												
NYHA class	X							X	X	X	X		
Medical/surgical history	X												
Physical examination	X									X			X ⁽⁷⁾
Height	X												
Weight	X	X	X	X	X	X	X	X	X	X	X		X
BP and heart rate	X	X	X	X	X	X	X	X	X	X	X		X
12-lead ECG ⁽²²⁾	X												
K ⁽⁸⁾	L ⁽⁹⁾	L	L&C	L	L	L	L	L&C	L&C	L&C	L&C		L
Serum chemistry	L ⁽¹⁰⁾ &C ⁽¹¹⁾	L ^(12,13)	C	L ⁽¹³⁾	L ⁽¹³⁾	L ⁽¹³⁾	L ⁽¹³⁾	C	C	C	C		L

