2.10.2 Secondary Endpoint Analyses

Key secondary efficacy endpoints will be tested sequentially in the order listed below (i.e. fixed-sequence method to preserve the familywise type I error rate) using the full analysis set, and will be summarized descriptively through the calculation of point estimates by treatment group along with 95% confidence intervals (CI) for the treatment differences.

For each key secondary endpoint, the primary analysis will use only data through June 24, 2021. A sensitivity analysis that includes all data will also be performed for each key secondary endpoint.

The following lists the secondary endpoints and the analysis methods to be used:

- Hyperkalemia events: The time to the first event of hyperkalemia with a serum K+ value >5.5 mEq/L, as per the measured values from the central or local laboratories, is analysed using a Cox proportional hazards regression model. The treatment difference will be reported as hazard ratio (HR) with 95% CI and p-value from a Wald-type test considering the null hypothesis that the HR is equal to 1. The event probabilities will be estimated using the Aalen-Johansen estimator of the cumulative incidence function accounting for competing events such as death.
- Durable enablement to stay on the MRA target dose (50 mg spironolactone or eplerenone): The time to the first event of reduction of the MRA dose below target is analysed using a Cox proportional hazards regression model. The treatment difference will be reported as hazard ratio (HR) with 95% CI and p-value from a Wald-type test considering the null hypothesis that the HR is equal to 1. The event probabilities will be estimated using Aalen-Johansen estimator of the cumulative incidence function accounting for competing events such as death.

Note: Discontinuation of the target dose for at least 14 days (or less if at the EoS) is required to confirm this endpoint.

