2.12 Baseline and Screening Definitions

2.12.1 Baseline

Unless otherwise specified, Baseline is defined as the value of a variable at the Day 1/Baseline Visit. If there is a missing value at the Day 1/Baseline Visit, Baseline is defined as the last available non-missing value on or before and ≤ 10 days prior to the first dose of blinded study medication.

For randomized but not treated subjects, Baseline is defined as the value at the Day 1/Baseline Visit; if missing, it is defined as the last available non-missing value on or before and ≤ 10 days prior to the date of randomization

Some laboratory tests are assessed by both the central laboratory and a local laboratory. In these cases, the following baseline values are defined:

- Local Baseline (Bsl_L) is defined as above using only local values
- Central Baseline (Bsl_C) is defined as above using only central values

- Central/Local Baseline (Bsl_CL) is defined as the Central Baseline (Bsl_C) if available, and as the Local Baseline (Bsl_L) if the Central Baseline is missing
- Local/Central Baseline (Bsl_LC) is defined as the Local Baseline (Bsl_L) if available, and as the Central Baseline (Bsl_C) if the Central Baseline is missing

In general, if an analysis includes only local laboratory test results for a specific laboratory test value, Bsl_L is used to calculate change from Baseline and is used as the baseline covariate in models; if the analysis includes only central laboratory test results, Bsl_C is used; if the analysis includes both central and local test results, Bsl_CL or Bsl_LC is used.

Tables and figures will specify what baseline is being used for the table or figure.

The following are specific exceptions to these rules:

- For eGFR, Bsl_CL is defined differently than for other laboratory parameters. The definition is: the value of the Central Baseline (Bsl_C); if missing, the value of the Local Baseline (Bsl_L); if missing, the value at Day 3, with preference for the central value
- Urine ACR is assessed only by the central laboratory, and is collected only during Run-in, at Day 3, Week 2, Week 18, and at each 3-month visit during the Double-blinded Treatment Phase. For analyses of proteinuria, Baseline is defined as the central value of urine ACR at the Day 3 Visit.

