2.13 Study Day and Visit Windows

The first date of dosing with the study medication (patiromer/placebo) will be used as the Reference Date for Study Day calculation.

The Study Day for date of first dosing is Day 1. The Study Day for all other study events is defined as follows:

- If a date is prior to the Reference Date, Study Day is defined as [date] - [Reference Date], so the Study Day for the day before date of first dose is defined as Day -1.
- If a date is on or after the Reference Date, Study Day is defined as [date] - [date of blinded study drug] +1; hence, the Study Day for the day after first dose is defined as Day 2.

Unless otherwise specified, summaries by visit will use the visit weeks/months reported in the database and include the results collected at scheduled visits.

The analyses which are not limited to scheduled visits (e.g. adverse events, incidence of laboratory test values within a given range, and time to event analyses), will include all available values of the variable of interest, irrespective of whether it was collected at a scheduled or unscheduled visit. For central laboratory data, the visit information from the central laboratory will be used to determine whether a visit is scheduled or unscheduled.

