2.17 Safety Analyses

Statistical analyses will be descriptive in nature and will not be routinely tested for statistical significance. Safety analyses will be based upon the clinical database only. Events recorded in the safety database will be reconciled with the clinical database prior to database lock.

The primary safety analyses will be conducted using all data. Some sensitivity analyses using the data cutoff as June 24, 2021 may be undertaken, as appropriate.

For subjects who were in the Run-in Phase twice, data from the second Run-in will be summarized. Data from the first Run-in will be included in listings only.

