2.17.1 Adverse Events

Adverse events (AEs) and serious adverse events (SAEs) coded using MedDRA (MedDRA version 23.0 or an updated version), including all-cause mortality, will be summarized descriptively.

AE summaries will be provided separately for the Run-in Phase and the Blinded Treatment Phase in the SS.

AE summaries will consist of counts (%) by MedDRA SOC and PT in the Run-in Phase, and by MedDRA SOC, PT and treatment arm in the Treatment Phase. The following types of AEs will be summarized:

- All treatment emergent adverse events (TEAEs)
- TEAEs by severity
- TEAEs related to study medication (patiromer/placebo)
- TEAEs leading to study medication discontinuation (patiromer/placebo)
- SAEs
- SAEs related to study medication (patiromer/placebo)

AE summaries will also be presented in the Run-in Phase Set.

A listing of AEs will be provided, to include verbatim term, preferred term (PT), system organ class (SOC), intensity/severity, relationship to patiromer/placebo, whether serious, onset/end date, action taken and outcome of event.

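### The only named Treatment Phase count of low serum K+ uses central laboratory results alone, so it omits the planned Day 3 to Week 6 readings and very likely undercounts affected subjects

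*SAP*

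**What the plan says.** SAP 2.17.2 sets the source of the threshold table: "The incidence of central laboratory test results in ranges of interest will be summarized by treatment group in the SS". The low-K+ cut-offs it names are 3.0, 3.5 and 3.8 mEq/L, in a list expressly left open to additions. The same section commits to subject listings from both laboratories, covering scheduled and unscheduled visits.

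SAP 2.13 gives a general rule for analyses not tied to scheduled visits. It covers the "incidence of laboratory test values within a given range, and time to event analyses), will include all available values of the variable of interest", whether or not the visit was scheduled. It does not name the laboratory, but adds: "For central laboratory data, the visit information from the central laboratory will be used to determine whether a visit is scheduled or unscheduled". SAP 2.12.1 foresees single-source analyses: "if the analysis includes only central laboratory test results, Bsl_C is used".

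The Schedule of Events and Protocol 8.2.2 to 8.2.5 and 8.3 give local K+ only at Day 3, Weeks 1, 2 and 6 and unscheduled visits. Protocol 8.2.6, 8.4 and 8.6 add a central K+ at Week 18, every 3 months, at EoS/ET and at the Potassium Assessment Visit. Unscheduled visits are part of routine management: "unscheduled weekly or monthly visits should occur until stability returns" (Study Schema, note e).

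Elsewhere the SAP accepts local values. The primary analysis uses local K+ only (2.10.1), and the first key secondary endpoint counts values "as per the measured values from the central or local laboratories" (2.10.2).

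**The concern.** Low K+ is an expected risk of a potassium binder, and the protocol's dosing text sets out to avoid it. Yet the one named Treatment Phase table with low-K+ thresholds draws on none of the four planned visits in the six weeks after randomization and on few, if any, unscheduled readings. Apart from EoS/ET and the Potassium Assessment Visit, the first planned post-baseline central K+ is Week 18, which with its window is day 96 to 126 (18 × 7 = 126; 126 − 30 = 96).

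Because Protocol 6.7.1.2 reduces study drug once hypokalemia appears, an early low local value may have resolved before any central draw. Subjects enrolled late fare worst. Their only central readings may be EoS, before which SAP 2.2 says many sites had already titrated or stopped study drug, and the Potassium Assessment Visit, which follows the end of dosing.

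High K+ is largely covered by the hyperkalemia endpoints in SAP 2.10.2 and 2.10.3, so the gap is mainly on the low side. At stake is the absolute incidence of low K+ shown to readers of the safety tables.

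**Working it through.** The plan gives no low-K+ rate, mean K+ level or within-subject correlation, so there is no figure of its own to reproduce. The check has a part that needs no assumption and an illustration that does.

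**1. Direction (no assumption).** Let C be the set of subjects with at least one low central value and A the set with at least one low value when local readings are added. C is contained in A, so with one denominator the central-only count cannot be higher. It is lower as soon as one subject is low only on a local reading. This still holds if the central value takes precedence wherever both laboratories report at a visit.

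**2. Visits with a central K+.** Scheduled post-baseline visits, Potassium Assessment Visit left out:

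| Follow-up | All visits | With central K+ |
|---|---|---|
| To Week 6, then EoS | Day 3, Weeks 1, 2, 6, EoS = 5 | EoS = 1 |
| To Week 18, then EoS | 6 | 2 |
| To about Week 44 (18 + 13 + 13), then EoS | 8 | 4 |

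Counting the Potassium Assessment Visit gives 2 of 6, 3 of 7 and 5 of 9.

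**3. Illustration of size (assumed inputs).** Model each reading as mean + subject effect + visit error. The assumed mean is 4.3 to 4.8, SD 0.4 to 0.6 and correlation 0.3 to 0.7, with no titration and no unscheduled visits. The plan's SD of 0.5 is for change in K+, so the SD of the level is an assumption too. With q the chance of a low reading given the subject effect, P(k) = E[1 − (1 − q)^k], and the share captured is P(central visits) / P(all visits).

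| Central / all | Below 3.5 | Below 3.8 |
|---|---|---|
| 1 / 5 | 20–41% | 22–49% |
| 2 / 6 | 34–59% | 36–66% |
| 4 / 8 | 51–75% | 54–81% |

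Example at 2 of 6 with mean 4.6, SD 0.5, correlation 0.5, below 3.5: P(2) = 2.6% and P(6) = 6.2%, so about 42% is captured.

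**4. Is k/n a floor?** For exchangeable readings, each extra reading adds no more new cases than the one before, so P(k)/P(n) ≥ k/n: 20%, 33% and 50%. If early K+ differs from later K+, this fails. In the same example, shifting the four early means by −0.2 to +0.3 mEq/L moves the captured share from 22% to 81%, so it can fall below 33%.

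**5. Comparison between arms.** With means 0.116 mEq/L apart (the plan's design difference), the risk ratio for a value below 3.5 is 1.32–2.77 central-only and 1.26–2.74 with all values, across every setting and visit pattern tried. The central-only ratio was never the smaller of the two.

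**6. Side effects of a combined table.**
- Paired values: in the example, counting a subject if either value at a two-laboratory visit is low raises the share ever below 3.5 by about 9–18%, if 10–50% of visit-level variance is laboratory-specific (assumed).
- Unequal testing: on a base of 6 readings with identical true K+, one extra reading per subject in one arm raises its count by 6–16%, and two extra by 12–32%.

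**The case against.** The other side has real points.

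- **The data are not lost.** Local and unscheduled values will be listed by subject under SAP 2.17.2. This stands, but a listing is not a count by arm.
- **Adverse events cover low K+.** Protocol 10.5.4 addresses reporting at K+ below 4.0 mEq/L, wider than the 3.8 cut-off, and SAP 2.17.1 tabulates events by preferred term, severity and arm. This also stands in part. It depends on investigator reporting, and the statement sits under the criterion about changes to study treatment; it yields no counts at 3.0, 3.5 or 3.8.
- **SAP 2.13 already calls for all available values.** A reader might go further and infer that 2.13 and 2.17.2 contradict each other. The documents do not support that: 2.13 is silent on laboratory source, has its own rule for unscheduled central data, and can be read as all available central values. The two need aligning.
- **Central-only is a sound convention.** Protocol 9.2 makes the central laboratory the default, the central laboratory screens K+ samples for hemolysis (Protocol 9.1.1), and the safety endpoint is defined as laboratory parameters not already used for efficacy. That supports keeping the central table. It is weak support for having no other, since the primary analysis rests on local K+ and, per Protocol 9.1.1, hemolysis gives falsely high values, not falsely low ones.
- **The open-ended list allows a fuller table.** True, but it commits to none.

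**Conclusion.** The point holds as a moderate, inexpensive correction. As written, the only named Treatment Phase low-K+ threshold count cannot exceed the all-values count and will very likely fall below it. That direction rests only on the visit schedule and on a shared denominator.

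The size is unknown. The captured shares above depend on assumed K+ levels and on exchangeable readings. A reader might take 20%, 33% and 50% as guaranteed minimums; they are not, because early and later K+ may differ.

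Two further inferences should be resisted. One is that the comparison between arms is diluted: the calculation showed no dilution in any setting tried. The other is that efficacy conclusions are at risk: the effect is confined to absolute low-K+ incidence in one descriptive safety table, and no primary or key secondary result changes. Nor do the documents suggest that low K+ goes unreported, given the listings and adverse event tables.

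**What to change.** In SAP 2.17.2, keep the central table and add one K+ range-incidence table by arm:

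- Use post-baseline local and central serum values from scheduled and unscheduled visits, counting each subject once per threshold.
- State the denominator, for example Safety Set subjects with at least one post-baseline value.
- Use one value per visit where both laboratories report, for example central preferred, as in the combined-data sensitivity analysis of SAP 2.10.1.
- Beside it, give a scheduled-visit-only count under the same pairing rule, and the number of readings per subject by arm.
- Show Potassium Assessment Visit readings separately, or state whether they count.

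In SAP 2.13, say which laboratory source the all-values rule refers to. No new data cut-off is needed, since SAP 2.17 already provides that "The primary safety analyses will be conducted using all data".

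The cost is wording in two sections and one table from data already collected. The downsides are variation between local laboratories across about 375 sites, possibly unequal unscheduled testing between arms (hence the scheduled-only count), and a less favourable low-K+ figure.

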1. INTRODUCTION AND BACKGROUND

1.1 Background of the Disease and Treatment Options

Twenty-six (26) million people worldwide have a diagnosis of HF [5]. In their Heart Disease and Stroke Statistics—2017 Update, the American Heart Association (AHA) reported data from National Health and Nutrition Examination Survey 2011–2014, which estimates that 6.5 million Americans ≥ 20 years of age have HF. Projections show that with improved survival and the aging of the population, the prevalence of HF in the US will increase 46% from 2012 to 2030, resulting in more than 8 million people ≥ 18 years of age with HF. Currently, HF accounts for nearly 1 million annual hospitalizations in the US and more than 3 million physician office visits. By 2030, 1 in every 33 US citizens will have a diagnosis of HF. Accordingly, it is in the public interest that therapies which have shown reductions in CV mortality, reductions in HF hospitalizations, and improvements in patient quality of life be used and optimally implemented [6,7,8]. Renal insufficiency is common in HF and is independently associated with increased all-cause and CV mortality [9]. However, in patients with advanced chronic kidney disease (CKD) (eGFR <30 mL/min/1.73 m 2) evidence-based strategies for improving CV outcomes remain almost unavailable [10].

HF mortality remains high. Approximately 50% of people diagnosed with HF will die within 5 years, but mortality rates have improved in the past 20 years, and this has been primarily because of evidence-based approaches to treating HF risk factors and comorbidities, as well as use of ACEi, beta-blocker, MRA, coronary revascularization, implantable cardioverter-defibrillators, and cardiac resynchronization therapeutic strategies [6].

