2.14 Handling of Missing Data

Missing data will be reflected primarily through the use of censoring for incomplete follow-up. The approach will depend on the particular analysis.

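### If the optional curves for the renal safety composite are drawn, Kaplan-Meier would censor non-renal deaths and slightly overstate absolute renal risk; Aalen-Johansen, already specified in SAP 2.10.2, would not

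*SAP*

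**What the plan says.** SAP 2.17.2 lists four components of the renal composite: an eGFR decline of more than 50%, ESRD, renal death and need for dialysis. The summary that will always be produced is a count with percentage ("or renal death, or need for dialysis at any time after randomization will be summarized by count"). The curves are conditional on enough subjects having the event; in that case "Kaplan-Meir curves for each treatment arm in the SS will also be provided". SAP 2.17 sets the status of all safety output: "Statistical analyses will be descriptive in nature and will not be routinely tested for statistical significance".

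SAP 2.17.2 does not say what happens to a subject who dies of a non-renal cause. The general rule in SAP 2.14 is "Missing data will be reflected primarily through the use of censoring for incomplete follow-up", followed by a statement that the approach will vary with the analysis. That rule concerns missing data and does not mention deaths. Protocol 12.9 lists the composite without naming an estimator.

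For key secondary endpoint 1 (serum potassium above 5.5 mEq/L), SAP 2.10.2 says event probabilities are "estimated using the Aalen-Johansen estimator of the cumulative incidence function accounting for competing events such as death". For key secondary endpoint 2 (staying on the MRA target dose) they are "estimated using Aalen-Johansen estimator of the cumulative incidence function accounting for competing events such as death". SAP section 3, on changes from the protocol, gives no reason for treating the renal composite differently.

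**The concern.** A subject who dies of a cardiovascular or other non-renal cause can no longer have the renal event. Kaplan-Meier handles that subject like one whose follow-up simply stopped, and so assumes the same future renal risk as in those still observed. The resulting curve describes a population in which nobody dies of anything else. Read as the proportion of patients who will have a renal event, it is too high, and increasingly so as deaths accumulate.

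The curve has some importance despite being optional. Treatment-phase duration varies by subject (Protocol 4.2) and the count with percentage ignores follow-up time, so the curve is the only planned display of this composite that accounts for time. Safety analyses also use all data, without the June 24, 2021 cutoff, so the curve covers the longest follow-up, where the overstatement is largest.

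**Working it through.** The plan states no event rate, risk or power for this composite, so there is no figure of its own to reproduce. The check illustrates the size of the gap under constant cause-specific hazards.

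**Inputs**
- Non-renal death hazard d. The mortality figure used is general heart failure background in Protocol 1.1: "Approximately 50% of people diagnosed with HF will die within 5 years". With a constant hazard, d = −ln(0.5)/5 = 0.139 per year. All of it is treated as non-renal. Range tried: 0.05 to 0.20.
- Renal event hazard r. Not in the documents; 0.04 per year is assumed. Range tried: 0.01 to 0.10.
- Follow-up t. Mean and median are not stated. The common end of study comes when 820 subjects have completed Week 6 (Protocol 4.2). Times from 6 weeks to 2 years are shown.

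**Formulas**
- Risk read from Kaplan-Meier: 1 − exp(−r·t).
- Aalen-Johansen cumulative incidence: r/(r+d) × [1 − exp(−(r+d)·t)].

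**Example at 2 years, r = 0.04, d = 0.1386**
- Kaplan-Meier: 1 − exp(−0.08) = 7.69%.
- Aalen-Johansen: 0.04/0.1786 × [1 − exp(−0.3573)] = 0.2239 × 0.3004 = 6.73%.
- Gap 0.96 points; ratio 1.14.

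**Results for r = 0.04**

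| Time | Kaplan-Meier | Aalen-Johansen, d = 0.139 | Gap (points) | Gap with d = 0.07 | Gap with d = 0.20 |
|---|---|---|---|---|---|
| 6 months | 1.98% | 1.91% | 0.07 | 0.03 | 0.10 |
| 1 year | 3.92% | 3.66% | 0.26 | 0.13 | 0.37 |
| 2 years | 7.69% | 6.73% | 0.96 | 0.51 | 1.33 |

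Over the full grid (r from 0.01 to 0.10, d from 0.05 to 0.20), the relative overstatement is about 0.3 to 1.2% at 6 weeks, 1 to 5% at 6 months, 2.5 to 10% at 1 year and 5 to 21% at 2 years. The largest absolute gaps are 0.23 points at 6 months, 0.88 at 1 year and 3.09 at 2 years. The 2-year maximum needs both the highest renal hazard and the highest mortality.

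**Unequal mortality.** Take r = 0.05 in both arms, with d = 0.10 in one and 0.15 in the other. At 2 years Kaplan-Meier shows 9.52% in both arms. Aalen-Johansen gives 8.64% and 8.24%. The overstatement is 0.88 points in one arm and 1.28 in the other.

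**Sampling error, for scale.** If all 410 subjects per arm were followed throughout, the binomial standard error √[p(1−p)/410] at the Kaplan-Meier risks above would be about 0.7 points at 6 months, 1.0 at 1 year and 1.3 at 2 years. With d = 0.139 the gap is below one standard error at each time.

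**The case against.** The strongest reply is that little depends on this curve. It appears only if events suffice, it is descriptive, and the count with percentage does not change with the estimator. All-cause mortality is summarised and every death is listed with its cause, so competing deaths stay visible. All of this stands.

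The size is also uncertain. The 0.139 hazard describes people diagnosed with heart failure in general, and Protocol section 2 reports lower-than-expected event rates in this trial. Follow-up may be short for many subjects. Under the main assumptions the gap is smaller than one arm's sampling error. This stands too, although the gap is systematic and sampling error is not.

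It can be said that Kaplan-Meier validly estimates a net risk with other deaths removed. That requires death to be independent of renal risk. Protocol 1.1 itself states that renal insufficiency in heart failure is independently associated with higher all-cause and cardiovascular mortality, so this defence is weak here.

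Several stronger readings are tempting but not supported:
- A reader might infer that the SAP avoids Kaplan-Meier everywhere else. Aalen-Johansen is visible for two endpoints only; the methods for other time-to-event endpoints in 2.10.3 and 2.10.4 are redacted.
- A reader might infer that Aalen-Johansen would make the renal figure comparable with the key secondary figures. Those use the full analysis set as randomised with data through June 24, 2021; safety uses treatment received and all data. They would still differ.
- A reader might infer that the SAP orders non-renal deaths to be censored. It does not say so; this follows from Kaplan-Meier and the composite's definition.
- A reader might infer that renal harm could be hidden. Within each arm the error in absolute risk runs upward.

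**Conclusion.** The point holds as a minor one. If the curves are produced as written, one minus Kaplan-Meier will overstate the actual cumulative incidence of the renal composite in both arms once non-renal deaths occur. The direction needs no assumption about rates. The size does: about 0.07 points at 6 months, 0.26 at 1 year and 1.0 at 2 years with a renal hazard of 0.04 and a death hazard of 0.139 per year, and about half that with a death hazard of 0.07. Neither hazard is known for this trial. Distortion between arms arises mainly if non-renal mortality differs by arm, which the documents give no ground to expect or to rule out. The composite's unconditional summary is sound on this point, and no test or decision is affected.

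**What to change.** In SAP 2.17.2, replace the sentence on Kaplan-Meier curves with one saying that, if events are sufficient, Aalen-Johansen cumulative incidence curves will be shown by arm in the Safety Set with non-renal death as the competing event, using the estimator already specified in 2.10.2. The same sentence should say how a death of undetermined cause is classed; 2.10.2 already counts such deaths as cardiovascular in the win ratio for hyperkalemia-related hard outcomes.

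The cost is one SAP sentence and minor programming. The estimator is specified for other endpoints, though the documents do not say that it has been programmed. No new data are needed, since date and primary cause of death are already to be listed under 2.17.3.
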